**Appendix 3. Study Procedures Table: Group B (ENTO + cytarabine + daunorubicin)**

Study Phase	Screening	Lead-in Cycle 0			Induction Cycle 1 (if needed Cycle 2)						Post-remission chemotherapy (up to Cycle 4)				Relapse	End of Treatment (EOT)	30-day Follow-up	Long Term Follow-up
		1	8	14	1	3	7	14	15 to count recovery	28	1	3	5	28				
Study Day	Screening	1	8	14	1	3	7	14	15 to count recovery	28	1	3	5	28	NA	NA	NA	NA
Window (day)	-14	NA	±2	±2	±2	±2	±2	±2	NA	±2	±2	±2	±2	±2	±2	±7	±7	± 4 weeks
General and Safety Assessments																		
Informed Consent	X																	
Medical & Medication History	X																	
Adverse Events/ Concomitant Medications	X	X	X	X	X	X	X	X		X	X	X	X	X		X	X	
Smoking status a	X	X			X						X							
Physical Exam b	X	X			X						X					X		
Vital Signs c	X	X	X	X	X	X	X				X					X		
Height and Weight d	X				X						X					X		
ECG e	X																	
ECHO/MUGA f	X							X		X								
Performance Status g	X	X						X		X				X		X		
Overall survival, leukemia treatments, and other malignancies																		X (every 6 months)
Chest X-ray	X																	
Study Treatment																		
ENTO Administration h,i		X	X	X	X	X	X	X		X	X	X	X	X				
IV daunorubicin j					X	X												
IV cytarabine h,i					X	X	X				X	X	X					

Study Phase	Screening	Lead-in Cycle 0			Induction Cycle 1 (if needed Cycle 2)						Post-remission chemotherapy (up to Cycle 4)				Relapse	End of Treatment (EOT)	30-day Follow-up	Long Term Follow-up
		1	8	14	1	3	7	14	15 to count recovery	28	1	3	5	28				
Study Day	Screening	1	8	14	1	3	7	14	15 to count recovery	28	1	3	5	28	NA	NA	NA	NA
Window (day)	-14	NA	±2	±2	±2	±2	±2	±2	NA	±2	±2	±2	±2	±2	±2	±7	±7	±4 weeks
Laboratory Assessments																		
Chemistry j,k	X	X	X	X			X	X		X				X		X		
Hematology k,r	X	X	X	X			X	X	X	X				X	X	X		
Coagulation k	X			X			X	X		X				X		X		
Urinalysis	X																	
Serum Pregnancy Test and FSH l	X																	
Urine Pregnancy Test m		X			X						X					X		
HIV/HBV/HCV	X																	
Sparse PK n		X		X		X		X		X			X	X				
Intensive PK o			X				X											
Bone Marrow Assessments																		
Biopsy p	X			X				X		X					X	X		
Aspirate q	X			X				X		X				X	X	X		

- a Collect smoking status at screening and Day 1 of each cycle.
- b After discharge from the hospital, a focused physical exam may be completed at the Investigator's discretion. During post-remission chemotherapy, a physical exam is to be completed on Cycle 1 Day 1 and Cycle 3 Day 1.
- c Vital signs include measurement of blood pressure, respiratory rate, pulse, temperature, and oxygen saturation level. Vital signs may be measured daily during hospitalization and at the Investigator's discretion after discharge from the hospital.
- d Height and weight will be measured at screening. Only weight will be measured on Day 1 of each induction cycle, Day 1 of each post-remission chemotherapy cycle, and at EOT.
- e ECG is required at Screening and may be performed at the Investigator's discretion following enrollment.
- f An ECHO or MUGA must be performed at screening and if applicable, prior to starting induction Cycle 2 (on Cycle 1 Day 14 or 28).
- g During post-remission chemotherapy, performance status to be completed on Cycle 2 Day 28 and Cycle 4 Day 28.
- h ENTO will be administered BID on Days 1-14 as a single agent in Cycle 0 then in combination with IV daunorubicin (Days 1-3) and IV cytarabine (Days 1-7) during induction chemotherapy of every 28-day cycle (Cycle 1 and up to Cycle 2). Subjects are to continue receiving ENTO BID as they are awaiting disease assessment results.

- i During post-remission chemotherapy, subjects will receive 2-4 cycles of 3g/m^2 HiDAC administered every 12 hours on Days 1, 3, and 5 (≤ 60 years of age) or 1g/m^2 HiDAC administered once daily on Days 1-5 (> 60 years of age) in combination with ENTO BID on Days 1-28.
- j Include Total CPK at screening, Day 14 of induction Cycle 1 (and Cycle 2, if applicable), Day 28 of post-remission chemotherapy Cycles 1 and 3, and EOT.
- k During post-remission chemotherapy, collect Chemistry, Hematology, and Coagulation on Day 28 of Cycles 1 and 3 only.
- l A negative serum pregnancy test is required for female subjects (unless surgically sterile or post-menopausal). Female subjects with medically documented ovarian failure must also have serum FSH levels within the institutional post-menopausal range.
- m For females of childbearing potential, urine pregnancy tests will be done on Day 1 of each cycle and at EOT.
- n Peripheral blood samples for sparse PK will be collected at pre-dose and 2hrs post-dose of ENTO on Cycle 0 Days 1 and 14, Days 14 and 28 of each induction cycle, and Days 5 and 28 of each post-remission chemotherapy cycle. Sparse PK will also be collected at pre-dose, 2, and 4 hours post-dose of ENTO on Day 3 of each induction cycle.
- o Peripheral blood samples for intensive PK will be collected on Cycle 0 Day 8 and induction Cycle 1 Day 7 at 0 (pre-dose), 1, 2, 3, 4, 6, 8, and 12 hours post-dose of ENTO.
- p A bone marrow biopsy will be performed at screening (within 21 days before the first administration of study treatment), Cycle 0 Day 14, Day 14 of each induction cycle (if hypocellular on Day 14, must repeat on Day 28 or within 21 days as blood counts recover prior to proceeding to post-remission chemotherapy or SCT), relapse, and EOT (if not performed within the last 2 weeks) for disease assessment. Subjects with cytogenetic and molecular mutations at screening must have cytogenetic and molecular mutation testing repeated at Cycle 0 Day 14, Cycle 1 Day 14 (or at count recovery), relapse, and EOT.
- q A bone marrow aspirate (~8mL) will also be collected for disease assessment at the bone marrow biopsy time-points noted above as well as post-remission chemotherapy Cycle 2 Day 28 and Cycle 4 Day 28 or as clinically indicated. Biopsy will be used in the event the aspirate cannot be collected or analyzed.
- r For subjects without evidence of residual leukemia on Day 14 of induction chemotherapy, local hematology (complete blood count) to be collected daily from Day 15 of induction chemotherapy until complete blood count demonstrates recovery.

## **Appendix 4. Pregnancy Precautions, Definition for Female of Childbearing Potential, and Contraceptive Requirements**

### **1) Definitions**

#### **a) Definition of Childbearing Potential**

For the purposes of this study, a female born subject is considered of childbearing potential following the initiation of puberty (Tanner stage 2) until becoming post-menopausal, unless permanently sterile or with medically documented ovarian failure.

Women are considered to be in a postmenopausal state when they are  $\geq 54$  years of age with cessation of previously occurring menses for  $\geq 12$  months without an alternative cause. In addition, women of any age with amenorrhea of  $\geq 12$  months may also be considered postmenopausal if their follicle stimulating hormone (FSH) level is in the postmenopausal range and they are not using hormonal contraception or hormonal replacement therapy and are without an alternative medical cause for amenorrhea.

Permanent sterilization includes hysterectomy, bilateral oophorectomy, or bilateral salpingectomy in a female subject of any age.

#### **b) Definition of Male Fertility**

For the purposes of this study, a male born subject is considered fertile after the initiation of puberty unless permanently sterile by bilateral orchidectomy or medical documentation.

### **2) Contraception Requirements for Female Subjects**

#### **a) Study Drug Effects on Pregnancy and Hormonal Contraception**

ENTO is contraindicated in pregnancy as a malformation effect is unknown, taking into consideration class effects, genotoxic potential, or a strong suspicion of human teratogenicity/fetotoxicity in early pregnancy based on non-clinical data. ENTO has insufficient data to exclude the possibility of a clinically relevant interaction with hormonal contraception that results in reduced contraception efficacy. Please refer to the latest version of the investigator's brochure for additional information.

#### **b) Contraception Requirements for Female Subjects of Childbearing Potential**

The inclusion of female subjects of childbearing potential requires the use of highly effective contraceptive measures. They must have a negative serum pregnancy test at Screening and a negative urine pregnancy test on the Baseline/Day 1 visit prior to enrollment. Pregnancy tests will be performed at monthly intervals thereafter. Female subjects must agree to one of the following methods from Screening until 30 days (Group A ENTO monotherapy) or 6 months (Group B ENTO + cytarabine + daunorubicin) following the end of relevant systemic exposure.

Individual Methods	Combination Methods	
	Hormone Methods (choose one and use with a barrier method)	Barrier Methods (use both OR choose one and use with a hormone method)
Intrauterine Devices (IUDs) 
 
Copper T 380A IUD*,**
 
LNg 20 IUD* ***
 
 Tubal Sterilization*	Estrogen and Progesterone 
 
Oral contraceptives*
 
Transdermal patch
 
Vaginal ring
 
 Progesterone 
 
Injection
 
Implant*
 
	
 
Diaphragm with spermicide* OR Cervical cap with spermicide
 
Male condom (with* or without spermicide*)
 

Partner's vasectomy must be used with a hormone or barrier method.		

Abbreviation: IUD = intrauterine device

\* Approved in Japan

\*\* Sold in Japan as Copper T 380 IUD

\*\*\* Sold in Japan as Minera 52mg

Female subjects must also refrain from egg donation and in vitro fertilization during treatment and until at least 30 days (Group A) or 6 months (Group B) after the end of relevant systemic exposure.

### 3) Contraception Requirements for Male Subjects

It is theoretically possible that a relevant systemic concentration may be achieved in a female partner from exposure of the male subject's seminal fluid. Therefore, male subjects with female partners of childbearing potential must use condoms during treatment and until 90 days (Group A) or 6 months (Group B) after the end of relevant systemic exposure. Additional contraception recommendations should also be considered if the female partner is not pregnant.

Male subjects must also refrain from sperm donation during treatment and until at least 90 days (Group A) or 6 months (Group B) after the end of relevant systemic exposure.

### 4) Unacceptable Birth Control Methods

Birth control methods that are unacceptable include periodic abstinence (eg, calendar, ovulation, symptothermal, post-ovulation methods), withdrawal (coitus interruptus), spermicides only, and lactational amenorrhea method (LAM). Female condom and male condom should not be used together.

### 5) Procedures to be Followed in the Event of Pregnancy

Subjects will be instructed to notify the investigator if they become pregnant at any time during the study, or if they become pregnant within 30 days (Group A) or 6 months (Group B) of last study drug dose. Subjects who become pregnant or who suspect that they are pregnant during the study must report the information to the investigator and discontinue study drug immediately. Subjects whose partner has become pregnant or suspects she is pregnant during the study must report the information to the investigator. Instructions for reporting pregnancy, partner pregnancy, and pregnancy outcome are outlined in Section 7.7.

**Appendix 5. Performance Scales: Karnofsky & ECOG Scores {Oken 1982}**

Karnofsky Status	Karnofsky Grade	ECOG Grade	ECOG Status
Normal, no complaints	100	0	Fully active, able to carry on all pre-disease performance without restriction
Able to carry on normal activities. Minor signs or symptoms of disease	90	0	Fully active, able to carry on all pre-disease performance without restriction
Normal activity with effort	80	1	Restricted in physically strenuous activity but ambulatory and able to carry out work of a light or sedentary nature, eg, light house work, office work
Care for self. Unable to carry on normal activity or to do active work	70	1	Restricted in physically strenuous activity but ambulatory and able to carry out work of a light or sedentary nature, eg, light house work, office work
Requires occasional assistance, but able to care for most of his needs	60	2	Ambulatory and capable of all selfcare but unable to carry out any work activities. Up and about more than 50% of waking hours
Requires considerable assistance and frequent medical care	50	2	Ambulatory and capable of all selfcare but unable to carry out any work activities. Up and about more than 50% of waking hours
Disabled. Requires special care and assistance	40	3	Capable of only limited selfcare, confined to bed or chair more than 50% of waking hours
Severely disabled. Hospitalisation indicated though death nonimminent	30	3	Capable of only limited selfcare, confined to bed or chair more than 50% of waking hours
Very sick. Hospitalisation necessary. Active supportive treatment necessary	20	4	Completely disabled. Cannot carry on any selfcare. Totally confined to bed or chair
Moribund	10	4	Completely disabled. Cannot carry on any selfcare. Totally confined to bed or chair
Dead	0	5	Dead

## **Appendix 6. Modified International Working Group Criteria for AML**

Assessment of clinical response in Group B will be made according to the International Working Group criteria {Cheson 2003}. The major criteria for judging response will include physical examination and examination of blood and bone marrow. All laboratory studies that are abnormal prior to study will be repeated to document the degree of maximal response.

### **Early Treatment Assessment (ETA)**

- Evaluation is made at approximately 7-10 days after completing the last dose of the initial course of treatment (i.e. Cycle 1 Day 14)
- Guides subsequent treatment (eg, need for or timing of second induction course)

### **Morphologic Complete Remission (CR)**

CR requires all of the following:

- < 5% blasts in bone marrow aspirate
- Neutrophils  $\geq 1,000/\mu\text{L}$
- Platelets  $\geq 100,000/\mu\text{L}$
- No extramedullary disease
- No blasts with Auer rods detected

### **Cytogenetic Complete Remission (CRc)**

CRc requires all of the following:

- < 5% blasts in bone marrow aspirate
- Neutrophils  $\geq 1,000/\mu\text{L}$
- Platelets  $\geq 100,000/\mu\text{L}$
- No extramedullary disease
- No blasts with Auer rods detected
- Reversion to a normal karyotype with an abnormal karyotype at the time of diagnosis

### **Morphologic CR with incomplete blood count recovery (CRi)**

CRi requires all of the following:

- < 5% blasts in bone marrow aspirate
- Neutrophils < 1,000/uL or Platelets < 100,000/uL
- No extramedullary disease
- No blasts with Auer rods detected

### **Partial Remission (PR)**

PR requires all of the following:

- $\geq 50\%$  decrease in blasts in bone marrow aspirate to a range of 5-25%
- Neutrophils  $\geq 500$ /uL
- Platelets  $\geq 50,000$ /uL

### **Treatment Failure (TF)**

Treatment failure will be classified as one of the following:

- Resistant disease: Failure to achieve a complete remission (CR, CRc, or CRi) or partial remission. Subjects who survive  $\geq 7$  days following completion of initial treatment, with evidence of persistent leukemia by blood and/or bone marrow examination.
- Death in Aplasia: Subjects who survive  $\geq 7$  days following completion of initial treatment, but dies while cytopenic, with an aplastic or hypoplastic marrow obtained within 7 days of death, without evidence of persistent leukemia
- Death from Indeterminate cause: Subjects who die before completion of treatment or < 7 days following completion of initial treatment; subjects who die  $\geq 7$  days following completion of initial treatment with no peripheral blood blasts, but no bone marrow examination is available; subjects who fail to complete the first cycle of therapy

## Relapse

Relapse is defined as:

- Evidence of morphologic relapse with the reappearance of leukemic blasts in the peripheral blood, blasts with auer rods,  $\geq 5\%$  blasts in the bone marrow, or evidence of extramedullary disease not attributable to any other cause. In the setting of recent treatment, if there are no circulating blasts and the bone marrow contains 5-20% blasts, a bone marrow biopsy should be repeated within 1 week to distinguish relapse from bone marrow regeneration.
- The reappearance of cytologically proven extramedullary disease also indicates relapse. Reappearance of a cytogenetic abnormality is considered a cytogenetic relapse. Evidence of bone marrow morphologic involvement or extramedullary disease required.

## LIST OF ABBREVIATIONS

AE	adverse event
AML	acute myeloid leukemia
ATC	Anatomical-Therapeutic-Chemical classification
BID	bis in die (twice a day)
BLQ	below the limit of quantitation
cm	centimeter
CR	complete remission
CRc	cytogenetic complete remission
CRi	morphologic CR with incomplete blood count recovery
CRF	case report form
CRO	contract research organization
CSR	clinical study report
CTCAE	Common Terminology Criteria for Adverse Events
DBP	diastolic blood pressure
DLT	dose limiting toxicity
ECG	electrocardiogram
ECOG	Eastern Cooperative Oncology Group
eCRF	electronic case report form(s)
EFS	event free survival
ENTO	Entospletinib
EOS	end of study
EOT	end of treatment
ETA	early treatment assessment
FAB	French-American-British
FAS	full analysis set
FDA	(United States) Food and Drug Administration
HiDAC	high-dose cytarabine
g	gram
GCP	Good Clinical Practice (Guidelines)
Gilead	Gilead Sciences, Inc.
h, hr	hour
HLGT	high-level group term
HLT	high-level term
HSCT	hematopoietic stem cell transplant
ID	identification
ICH	international conference on harmonisation
IV	intravenous
kg	kilogram

---

LFS	leukemia free survival
LLT	lower-level term
LOQ	lower limit of quantitation
mg	milligram
MedDRA	Medical Dictionary for Regulatory Activities
NCI	National Cancer Institute
NIH	National Institutes of Health
NE	not evaluable
ORR	objective response rate
OS	overall survival
PD	progressive disease
PK	pharmacokinetic(s)
PR	partial remission
PT	preferred term
Q1	first quartile
Q3	third quartile
StD	standard deviation
SAE	serious adverse event
SAP	statistical analysis plan
SBP	systolic blood pressure
SE	standard error
SOC	system organ class
SOP	standard operating procedure
TEAE	treatment emergent adverse event
TF	Treatment failure
TFL	tables, figures and listings
TTR	time to response
uL	microliter
ULN	upper limit of the normal range
US	United States
WHO	World Health Organization

## 1. INTRODUCTION

This statistical analysis plan (SAP) describes the statistical analysis methods and data presentations to be used in tables, figures, and listings (TFLs) in a synoptic study report (CSR) for Study GS-US-429-4104. This SAP is based on Protocol GS-US-429-4104 Amendment 3 dated 23 August 2017 and the electronic case report form (eCRF). The SAP will be finalized before database finalization. Any changes made after the finalization of the SAP will be documented in the CSR.

The study was originally designed to evaluate the safety, tolerability, and pharmacokinetics of entospletinib (ENTO) in 2 stages: (1) ENTO monotherapy (Group A) for relapsed or refractory hematologic malignancies; (2) ENTO in combination with cytarabine and daunorubicin (Group B) for AML. However, per the Sponsor's decision, only the monotherapy stage is conducted with full enrollment of Group A, and the study will be terminated early without opening enrollment in Group B. The decision to terminate the study was not due to any safety concerns. Therefore, a synoptic CSR will be generated, and this SAP describes the analyses for the monotherapy part (Group A) only.

### 1.1. Study Objectives

#### 1.1.1. Primary Objectives

- To evaluate the safety and tolerability of ENTO monotherapy in Japanese subjects with relapsed or refractory hematologic malignancies
- To evaluate the safety and tolerability of ENTO in combination with cytarabine and daunorubicin (7+3) in Japanese subjects with previously untreated AML who are candidates for chemotherapy

#### 1.1.2. Secondary Objectives

- To evaluate the pharmacokinetics (PK) of ENTO in Japanese subjects with relapsed or refractory hematologic malignancies
- To evaluate the PK of ENTO in Japanese subjects with previously untreated AML who are candidates for chemotherapy
- To evaluate the safety and tolerability of ENTO in combination with age-adjusted high-dose cytarabine (HiDAC) in Japanese subjects with previously untreated AML who are candidates for chemotherapy

### 1.2. Study Design

This is a Phase 1b, open-label, multicenter study evaluating the safety, tolerability, and PK of ENTO as monotherapy in Japanese subjects with relapsed or refractory hematologic malignancies and in combination with cytarabine and daunorubicin (7+3) in Japanese subjects

with previously untreated AML. The study was originally designed for 2 stages sequentially: (1) ENTO monotherapy in subjects with relapsed or refractory hematologic malignancies (Group A); (2) ENTO in combination with cytarabine and daunorubicin (7 + 3) in subjects with untreated AML (Group B). Up to 24 subjects will be dosed in 2 groups using a rolling 6 design to evaluate 12 subjects for DLT assessment. However, per the Sponsor's decision, it was decided to only enroll subjects into Group A. The planned dose levels for Group A are:

Dose Level	Entospletinib
-1	200 mg twice daily
0	400 mg twice daily

The first 6 subjects in Group A will be enrolled at dose level 0 (400 mg twice daily BID). Subjects will receive ENTO BID on Days 1-28 of every 28-day cycle and will continue on study treatment as long as the subject is experiencing clinical benefit and does not meet criteria for study treatment discontinuation. When the sixth evaluable subject has completed the DLT assessment window (begins on Cycle 1 Day 1 and ends on Cycle 1 Day 28), the safety review team will evaluate the safety data from all enrolled subjects. During the DLT assessment window, subjects who fail to complete a total of 21 days of ENTO for reasons other than a DLT will not be evaluable for DLT assessment and may be replaced in a timely manner as determined by the Gilead Medical Monitor, the Japanese CRO Medical Monitor, and the Principal Investigator.

- If 0 or 1 out of the 6 subjects experiences a DLT, Group B will open and 6 subjects will be enrolled in Group B at dose level 0
- If  $\geq 2$  out of the 6 subjects experience a DLT, 6 additional subjects will be enrolled in Group A at the reduced dose level -1 (200 mg BID) and Group B will not open.

The schedules of study procedure are provided in [Appendix 1](#).

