#### 3.2.1. Dose Limiting Toxicities

The DLT assessment window for Group A begins on Cycle 1 Day 1 and ends on Cycle 1 Day 28 and for Group B begins on lead-in Cycle 0 Day 1 and ends 28 days from Cycle 1 Day 1 of induction chemotherapy. The subjects in this study should be in hospital during the DLT assessment window, and the window for Group B may be expanded for bone marrow recovery as noted below. During the DLT assessment window, subjects who fail to complete a total of 21 days of ENTO (or in Group B, miss any doses of cytarabine and daunorubicin) for reasons

other than DLT will not be evaluable for DLT assessment and additional (replacement) subjects may be enrolled in a timely manner to that dose level in order to provide adequate safety data, as determined by the Gilead Medical Monitor, the Japanese CRO Medical Monitor, and the Principal Investigator.

A Grade 4 non-hematologic toxicity attributable to ENTO will be considered a DLT with the exception of alopecia, nausea and vomiting controllable with anti-emetic therapy, line associated venous thrombosis, line associated infection and fatigue.

In subjects without bone marrow evidence of hematologic malignancy (eg, leukemia, lymphoma, or myeloma) by pathological examination, hematologic toxicity will be defined as failure to recover neutrophil count ( $ANC > 500/uL$ ) or platelet count ( $> 25000/uL$ ) within 28 days for Group A and within 8 weeks from chemotherapy initiation for Group B.

Subjects with transient Grade 4 electrolyte abnormalities that are not clinically significant and are correctable within 24 hours will not be considered DLTs.

Subjects with transient liver function test abnormalities (AST, ALT, bilirubin, or alkaline phosphatase) that resolve to  $\leq$  Grade 2 within 10 days will not be considered DLTs.

In general, infection will not constitute DLT unless it is felt that the infection resulted from unexpectedly complicated prolonged myelosuppression.

Toxicities that require temporary interruption of treatment with ENTO (but not permanent discontinuation) will not be considered DLTs unless the toxicity does not resolve to  $\leq$  Grade 2 within 10 days. Subjects in whom ENTO was suspended or dose reduced for a period of more than 10 days will be considered as having a DLT.

Once the sixth evaluable subject has completed the DLT assessment window, the safety review team will evaluate the safety data from all enrolled subjects..

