### **8.6.2. Adverse Events**

All AEs will be listed. The AE summarization will focus on treatment-emergent AEs. Treatment-emergent AEs are defined as AEs that onset in the period from the first dose of study treatment to 30 days after the permanent discontinuation of study treatment or that lead to permanent study treatment discontinuation.

AEs that occur before the first dose of study treatment or >30 days after study treatment discontinuation will be included in data listings.

AEs will be classified using Medical Dictionary for Regulatory Activities (MedDRA) with descriptions by System Organ Class, High-Level Group Term, High Level Term, Preferred Term, and Lower-Level Term. The severity of AEs will be graded by the investigator according to the CTCAE, Version 4.03 (<http://www.hrc.govt.nz/sites/default/files/CTCAE%20manual%20-%20DMCC.pdf>), whenever possible. If a CTCAE criterion does not exist for a specific type of AE, the grade corresponding to the appropriate adjective will be used by the investigator to describe the maximum intensity of the AE: Grade 1 (mild), Grade 2 (moderate), Grade 3 (severe), Grade 4 (life threatening), or Grade 5 (fatal). The relationship of the AE to study treatment will be categorized as related or unrelated.

Treatment-emergent AEs will be summarized by presenting the number and percentage of subjects with treatment-emergent AEs by severity grade. Subjects who report multiple treatment-emergent AEs under the same Preferred Term (or System Organ Class) are counted only once under the worst severity grade. The summary will be presented in decreasing frequency of System Organ Class and Preferred Term of the 'Total' column. Within the same frequency, the AEs are ordered in the alphabetical order of System Organ Class and Preferred Term. Separate listings and summaries will be provided for the following types of treatment-emergent AEs:

- Study treatment related AEs
- AEs with severity  $\geq$  Grade 3
- AEs leading to study treatment interruption and/or dose modification
- AEs leading to study treatment discontinuation
- Study treatment related SAEs
- DLT
- DLT rates and their 90% CI

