### 1.3. Sample Size and Power

There is no formal efficacy or safety hypothesis to be tested in this study, and therefore no formal size calculation was performed.

The rolling 6 design is implemented for the study. The first 6 subjects will be enrolled at dose level 0 in Group A. During the DLT assessment window, if 0 or 1 out of these 6 subjects experience DLTs in Group A, Group B will open and 6 subjects will be enrolled at dose level 0 in Group B. However, if 2 or more subjects experience DLTs in Group A, 6 additional subjects will be enrolled at dose level -1 in Group A and Group B will not open. Subjects who discontinue early for a non-DLT defined reason during the DLT assessment window will not be evaluable for DLT and may be replaced. The aforementioned subjects are DLT evaluable subjects.

With consideration for subject replacement, up to 24 subjects will be enrolled to the study.

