##### **3.1.2. Dose-Limiting Toxicity (DLT) Analysis Set**

DLT Analysis Set includes all subjects in the FAS who meet at least one of the following criteria:

- Receive at least 21 days of ENTO during the DLT assessment window (refer to Section 1.2).
- Experience a DLT during the DLT assessment window.

This analysis set will be used for analyses related to DLT.

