## **4. SUBJECT DISPOSITION**

### **4.1. Subject Enrollment and Disposition**

A summary of subject disposition will be provided by dose level based on FAS. This summary will present the number and percentage of subjects in the following categories:

- ENTO discontinuation
  - Reasons of ENTO discontinuation
- Included in the DLT analysis set
- Study discontinuation
  - Reasons of Study discontinuation

The denominator for the percentage calculation will be the total number of subjects in FAS corresponding to that column.

A data listing of subject enrollment to describe the site, subject number, date of first and last dose and dose level of ENTO, analysis set inclusion (FAS and DLT analysis sets), reasons for ENTO discontinuation, and reasons for study discontinuation will be provided.

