#### **7.1.7. Dose Limiting Toxicity**

Dose limiting toxicity (DLT) will be analyzed based on the DLT analysis set.

A listing of the DLT AEs will be provided by dose level, subject identification, actual dose amount prior to or on the start date of the AE, DLT terms from the investigators, CTCAE terms, and associated severity grade, if available.

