#### **7.7. Changes From Protocol-Specified Safety Analyses**

There are no deviations from the protocol-specified safety analyses.

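### The SAP plans only a listing for the primary endpoint, omits the DLT rate with 90% CI that the protocol requires, and declares no deviation; nor does it state why a subject is not DLT-evaluable

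*SAP*

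**What the plan says.** **Endpoint and planned analysis.** Protocol 8.1.2 makes the occurrence of DLTs the primary endpoint. Among the adverse event outputs, Protocol 8.6.2 lists "DLT rates and their 90% CI". Protocol 8.3 sets the exact binomial, two-sided, as the default method for 95% intervals on binary variables; 8.6.2 names no method for the 90% interval.

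**SAP.** Section 7.1.7 plans one output: "A listing of the DLT AEs will be provided by dose level". The summaries in SAP 7.1.6 include no DLT row. SAP 7.7 then states: "There are no deviations from the protocol-specified safety analyses". SAP 3 restricts efficacy to listings because only 9 subjects were enrolled, but promises tables as well as listings for safety.

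**Who is counted.** The Group A window is Cycle 1 Days 1 to 28. SAP 1.2 says "subjects who fail to complete a total of 21 days of ENTO for reasons other than a DLT will not be evaluable for DLT assessment". SAP 3.1.2 admits a subject who meets either of two conditions: "Receive at least 21 days of ENTO during the DLT assessment window", or a DLT within that window. Under Protocol 3.2.1, a toxicity that only interrupts ENTO is not a DLT if it falls to Grade 2 or lower within 10 days. The same section adds: "Subjects in whom ENTO was suspended or dose reduced for a period of more than 10 days will be considered as having a DLT". SAP 1.3 words evaluability differently: "Subjects who discontinue early for a non-DLT defined reason during the DLT assessment window will not be evaluable for DLT".

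**The concern.** A reader of the clinical study report would expect the primary endpoint as a number of subjects with a DLT, a denominator, a rate and an interval. The SAP gives the denominator in its disposition table ("Included in the DLT analysis set") and the events in a listing, and leaves the reader to combine them. The interval is planned nowhere. Because SAP 7.7 says nothing has changed, the report would also not disclose that a protocol analysis had been dropped.

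The denominator raises a second, smaller question. If a hold for drug toxicity can be too short to be a DLT and yet long enough to make the subject non-evaluable, toxicity itself can decide who is counted. No planned output states the reason for non-evaluability or the number of days dosed within the window. The exposure duration in SAP 4.2.1 runs from first to last dose and ignores interruptions, so it does not supply that number.

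**Working it through.** **1. The plan's own figure.** SAP 1.2 aims to assess 12 subjects for DLT: 6 in Group A at dose level 0 plus 6 in the next cohort = 12. This reproduces. SAP 1.3 states that no formal size calculation was performed, so there is no power or error rate to check.

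**2. The two documents side by side.**

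| Item | Protocol | SAP |
|---|---|---|
| DLT listing | 8.6.2: yes | 7.1.7: yes |
| DLT rate with 90% CI | 8.6.2: yes | none in 7.1.6 or 7.1.7 |
| Safety tables kept after early termination | not applicable | 3: yes |
| Departure declared | not applicable | 7.7: none |

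Neither SAP 7.1.6 nor 7.1.7 shows blacked-out text.

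**3. What the missing interval would show.** Exact two-sided 90% limits for x events in n subjects:

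- x = 0: upper limit = 1 − 0.05^(1/n).
- x = 1: lower limit = 1 − 0.95^(1/n); the upper limit p solves (1 − p)^n + n·p·(1 − p)^(n−1) = 0.05.

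The documents give neither the DLT count nor the number evaluable. Assuming n = 6 (the design target):

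- 0/6: 1 − 0.05^(1/6) = 0.393, so 0 to 39.3%.
- 1/6 = 16.7%: 1 − 0.95^(1/6) = 0.009, upper limit 0.582, so 0.9 to 58.2%.

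At the other end of the range, with all 9 enrolled subjects evaluable:

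- 0/9: 0 to 28.3%.
- 1/9 = 11.1%: 0.6 to 42.9%.

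**4. The evaluability gap in Group A.** Take one continuous hold of L whole days starting on Day s (s at least 2), with no other missed days. Days off in the window = min(L, 29 − s). Days dosed = 28 minus that.

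| Hold length L | Start day s | Days dosed in window | At least 21? |
|---|---|---|---|
| 7 | 2 or later | 21 or more | yes |
| 8 | 2–21 | 20 | no |
| 9 | 2–20 | 19 | no |
| 9 | 21 | 20 | no |
| 10 | 2–19 | 18 | no |
| 10 | 20 | 19 | no |
| 10 | 21 | 20 | no |
| 8–10 | 22 or later | 21 or more | yes |

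No hold in the table exceeds 10 days, so none is a DLT by duration. If the toxicity resolves to Grade 2 or lower within 10 days and meets no other DLT criterion, the subject enters the DLT Analysis Set by neither route. Checking every hold length from 1 to 28 days against every start day from 2 to 28 gives the same limits: lengths 8 to 10, starts on Days 2 to 21.

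**5. The edge of the window.** The 11th day of a hold falls on Day s + 10. For s = 18 that is Day 28, inside the window. For s = 19, 20 and 21 it is Day 29, 30 and 31, outside it. A hold of more than 10 days with those starts leaves 18, 19 and 20 days dosed in the window. Protocol 3.2.1 calls it a DLT, but SAP 3.1.2 requires the DLT to occur during the window, and neither says on which day such a DLT is dated.

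**6. SAP 1.3 against SAP 3.1.2.** If stopping early means stopping at any time before Day 28, a subject who stops after 21 to 27 days of ENTO for a non-DLT reason is non-evaluable under 1.3 but in the set under 3.1.2. If it means stopping before 21 days are reached, the two agree.

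**The case against.** **The evaluability rule is deliberate.** A minimum-exposure requirement is ordinary in a DLT design, and Protocol 3.2.1, SAP 1.2 and SAP 3.1.2 state it consistently. This stands. The gap in step 4 follows from the rule and is not a contradiction.

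**The information is mostly there.** With 9 subjects, the set size and the DLT listing allow a crude rate by hand. The reason for non-evaluability can largely be pieced together from set inclusion and dose dates (SAP 4.1), interruptions with reasons (4.2.1), the dose-modification listing (4.2.2) and events leading to interruption (7.1.6). Excluded subjects stay in the FAS safety outputs, and the safety review covers all enrolled subjects. This stands too, and makes the evaluability part a reporting aid only. It does not supply the interval or correct SAP 7.7.

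**Stronger readings that the documents do not support.**

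- A reader might infer that the gap understates the DLT rate. No frequency is given. If p is the DLT probability and q the probability of such a hold, replacement makes the expected rate among evaluable subjects p/(1 − q), slightly above p. With assumed values p = q = 10%, it is 0.10/0.90 = 11.1%. What can be lost from the primary analysis is a tolerability signal.
- A reader might want a sensitivity rate that adds the excluded subjects. They have no DLT, so they would enter as DLT-free with no minimum exposure. Adding three moves 1/6 = 16.7% to 1/9 = 11.1% and the upper limit for no events from 39.3% to 28.3%. That works against the concern.
- A reader might take SAP 1.3 as a firm contradiction of 3.1.2. It is one only on the first reading in step 6.
- A reader might see Table 5-1 as conflicting with the DLT definition. The table guides holding and resuming ENTO and calls itself guidance; Protocol 3.2.1 defines a DLT.

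**Conclusion.** The main point holds as a plain disagreement between the two documents. The protocol requires a DLT rate with a 90% interval, the SAP leaves it out, and the SAP says nothing was left out. It concerns the primary endpoint and should be put right. On the assumption of 6 evaluable subjects, the unreported upper limit would be 39.3% with no DLT and 58.2% with one.

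The secondary point holds in a limited form: exclusion from the DLT Analysis Set can be caused by toxicity, and no output says whether it was. It assumes one continuous hold, whole days (the documents do not say how a day with one of two doses counts) and no other DLT criterion met. Its size in this study is unknown. With 9 enrolled and 6 evaluable needed, up to 9 − 6 = 3 could be outside the set, but that is an inference and not a reported count.

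A reader might infer that this affected dose decisions. SAP 1 says Group B was not opened by sponsor decision and that termination was not for safety reasons, so the effect is on how the report is read.

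**What to change.** 1. **SAP 7.1.7.** Add the number and rate of subjects with a DLT on the DLT Analysis Set as defined, with a two-sided 90% CI. The exact binomial is in line with the default in Protocol 8.3. If the rate is left out, record and justify that in SAP 7.7.
2. **SAP 4.1 listing.** Add two columns: days of ENTO dosed in Days 1 to 28, taken from the dosing records, and the reason a subject is not DLT-evaluable. Show the count by reason over the FAS next to the DLT rate.
3. **Wording.** The sponsor should make SAP 1.3 consistent with SAP 1.2 and 3.1.2. The sponsor should also clarify how Protocol 3.2.1 and SAP 3.1.2 together classify a hold of more than 10 days that starts on Days 19 to 21. No DLT, dosing or evaluability rule is proposed here.

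The cost is one small table and two listing columns from data already collected. The analysis set, patients, visits and replacements do not change. If the SAP is already final, its Introduction provides for documenting the change in the clinical study report.
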